### 5.5.3 Dose De-Escalation Criteria

Dose de-escalations will proceed as follows after the occurrence of dose-limiting toxicity (DLT):

| Number of Patients with DLT at a Given Dose Level | De-Escalation Decision Rule                                                                                                                                                                       |
|----------------------------------------------------------|----------------------------------------------------------------------------------------------------------------------------------------------------------------------------------------------------------|
| 0 or 1 out of 6                                          | If Dose Level 0: If 0-1 patients experience a DLT move to the phase II portion at Dose Level 0.

If Dose Level -1: If 0-1 patients experience a DLT, move to the phase II portion at Dose Level -1 |
| ≥ 2 out of 6                                             | Dosing at this dose level will be stopped and 6 additional patients will be entered at the next lowest dose level, if available.                                                                         |

### 5.5.4 Toxicity, Response, and DLT Evaluations

All patients who receive any study treatment are evaluable for toxicity. Patients are evaluated from first receiving study treatment until a 30-day follow up after the conclusion of treatment or death.

All patients are evaluable for disease response unless they come off study due to treatment related adverse events(s) prior to completion of Cycle 2 and have not had any disease assessment.

A patient is evaluable for DLT assessment only if enrolled in the phase I portion and only during Cycle 1 of treatment. If the patient is not able to be treated on Day 1 of Cycle 2, then s/he is still considered in Cycle 1 active treatment and can experience a DLT. Once the patient has been treated in Cycle 2, s/he will no longer be evaluated for DLTs in all subsequent cycles.

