### **2.2 Secondary Objectives**

1. To determine the overall response rate (ORR) of patients with advanced or metastatic pancreatic cancer being treated with tosedostat and capecitabine combination therapy.
2. To determine the time-to-progression (TTP) of patients with advanced or metastatic pancreatic cancer being treated with tosedostat and capecitabine combination therapy.
3. To determine overall survival (OS) of patients with advanced or metastatic pancreatic cancer being treated with tosedostat and capecitabine combination therapy.
4. To determine CA19-9 response of patients with advanced or metastatic pancreatic cancer being treated with tosedostat and capecitabine combination therapy.

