### 5.4 Phase II Treatment Plan

Once the RP2D is determined, additional patients will be enrolled for a total of 36 evaluable patients (the patients from the RP2D level of phase I will be included in this group).

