## 11.0 DATA SUBMISSION SCHEDULE

Case report forms with appropriate source documentation will be completed according to the schedule listed in this section.

| Case Report Form                                       | Submission Schedule                                               |
|--------------------------------------------------------|-------------------------------------------------------------------|
| Original Consent Form                                  | Prior to registration                                             |
| Registration Form
Eligibility Form
On-Study Form | Prior to starting treatment                                       |
| Treatment Form
Correlatives Form                    | Every cycle                                                       |
| DLT Form                                               | End of Cycle 1                                                    |
| Toxicity Form                                          | Continuous                                                        |
| Treatment Summary Form                                 | Completion of treatment                                           |
| Follow Up Form                                         | Every 3 months for 1 year after end of treatment                  |
| Tumor Measurement Form                                 | Baseline, end of every even numbered cycles, and end of treatment |
| MedWatch Form                                          | See Section 7.0 for reporting requirements                        |

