## **14.0 STATISTICAL CONSIDERATIONS**

### **14.1 Sample Size**

In the phase I part of the study, a de-escalation 3+3 design is used to determine the recommended phase II dose of tosedostat when combined with capecitabine in patients with advanced or metastatic pancreatic adenocarcinoma. The minimal number of patients needed for the phase I part of the study is 6 patients assuming no DLT is observed in Dose Level 1. The maximal number of patients is 12 patients.

For the phase II part of the study, the primary endpoint of the study is to assess the progression-free survival (PFS) of the combination therapy. Based on historical data, the PFS of 2.0 months was observed with either 5-FU or capecitabine in the second-line setting, so a median PFS of 4 months for the combination regimen would be considered clinically meaningful for further development. With a sample size of 36 patients including 3-6 patients from the phase I portion, the study has power 0.80 to identify an increase of the median PFS (2.0 to 4.0 months) at a 0.05 significance level, assuming 12 months of accrual and 6 months of follow-up. We will consider this phase II part as a pilot study for the PFS as endpoint; therefore a sample size of 36 is adequate. We expect to enroll 3-4 patients per month; therefore it is feasible to recruit 36 patients within 1 year.

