### **14.2 Data Analysis**

PFS and OS will be estimated by Kaplan-Meier product limit method. The progression-

free survival and overall survival probabilities at certain time points (e.g. 3 months, 6 months) will be presented as well. The overall response rate (ORR) and CA19-9 response will be characterized by summary statistics (frequency and proportion). The logistic regression model will be considered to explore the predictive molecular biomarkers, the prognostic biomarkers for treatment response, and to investigate the correlation between genetic alterations and response to treatment.

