### **14.3 Interim Analysis**

After 10 evaluable patients have enrolled to the phase II portion of the study, an interim analysis will be conducted to look at response to date to assess for continuation of the study.

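### If the Section 5.5.4 evaluable set is used as the ORR denominator, ORR can only rise or stay the same against all treated patients; Section 14.2 should name all treated patients instead

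*Combined protocol and SAP*

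**What the plan says.** Section 5.5.4 defines two sets that bear on this point. For safety: "All patients who receive any study treatment are evaluable for toxicity". For efficacy: "All patients are evaluable for disease response unless they come off study due to treatment related adverse events(s) prior to completion of Cycle 2". The second sentence continues with a condition that must also hold, namely that the patient has had no disease assessment. A patient is therefore removed only when all of these coincide: off study, because of a treatment-related adverse event, before Cycle 2 is complete, and unassessed.

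The ORR objective in Section 2.2 is "To determine the overall response rate (ORR) of patients with advanced or metastatic pancreatic cancer being treated with tosedostat and capecitabine combination therapy". It defines no analysis set. Section 14.2 gives the analysis as "The overall response rate (ORR) and CA19-9 response will be characterized by summary statistics (frequency and proportion") and states no denominator.

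Section 14.3 uses the word evaluable without defining it: "After 10 evaluable patients have enrolled to the phase II portion of the study, an interim analysis will be conducted to look at response".

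A partial response under Section 12.4.1 needs a measured decrease from the baseline sum of diameters. Section 12.3 does not allow tumour markers alone to establish response. Section 12.1 sets response evaluation every 6 weeks, which is two 21-day cycles.

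**The concern.** The rule selects on the regimen's own toxicity. Someone who stops early for a related event, before any on-study scan, leaves the response-evaluable set. Someone who stops unscanned because of withdrawal or an unrelated event stays in. A death not related to treatment also stays in, while a treatment-related early death could be excluded. The more patients the combination drives off study early, the smaller the denominator, and a single-arm trial has no control arm to offset this.

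Such exits are foreseeable. The first scheduled on-study CT comes at the end of Cycle 2, and Sections 6.1, 6.1.3 and 6.2 each contain toxicity-related routes off study that could apply before then.

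What is at stake is the interpretation of a secondary endpoint, and a choice of denominator that would otherwise be made after the data are seen.

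**Working it through.** **Stated figure.** The documents give no ORR target, ORR sample size or ORR precision, so there is nothing to reproduce first.

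**Inputs.** The exclusion rule is from Section 5.5.4, the response definition from 12.4.1 and the bar on marker-only response from 12.3. The planned number is 36 (Sections 5.4 and 14.1). The number of responders *x* and the number excluded *k* are not in the documents. The values below are assumptions over a range.

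**Direction.** Let *n* be the number treated. Excluded patients have no on-study measurement and contribute nothing to *x*. The two rates are

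- all treated: x/n
- 5.5.4 set: x/(n − k)

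Since n − k ≤ n, x/(n − k) ≥ x/n, with equality only when x = 0 or k = 0. The ratio of the two rates is n/(n − k).

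**Size, with 36 treated.**

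| Responders (assumed) | All treated | k = 1 | k = 2 | k = 4 | k = 6 |
|---|---|---|---|---|---|
| 0 | 0% | 0% | 0% | 0% | 0% |
| 2 | 5.6% | 5.7% | 5.9% | 6.25% | 6.7% |
| 4 | 11.1% | 11.4% | 11.8% | 12.5% | 13.3% |
| 6 | 16.7% | 17.1% | 17.6% | 18.8% | 20.0% |

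For 6 responders and k = 4, 6/32 − 6/36 = 18.75 − 16.67 = 2.08 percentage points. For k = 6, 6/30 − 6/36 = 20.0 − 16.7 = 3.3 points. The Clopper-Pearson 95% interval for 6/36 is 6.4% to 32.8%.

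**Size, if 36 are response-evaluable and the excluded patients are replaced.** The comparison becomes x/36 against x/(36 + k). With 6 responders, 16.7% compares with 6/37 = 16.2%, 6/38 = 15.8% and 6/40 = 15.0%. The direction is the same.

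**Interim look.** If evaluable in 14.3 means response-evaluable, an assumed 2/10 = 20.0% would compare with 2/11 = 18.2% (k = 1) or 2/12 = 16.7% (k = 2).

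A plain all-treated rule at this look would do more harm than the exclusion. The look is triggered by enrolment, and Section 14.1 expects 3 to 4 patients per month. Six weeks is 42/30.4 = 1.38 months, so 1.38 × 3 = 4.1 to 1.38 × 4 = 5.5 patients would not yet be due a first scan if the look were run at the trigger. Scoring them as non-responders could turn 2/5 = 40% among about five assessable patients into 2/10 = 20%.

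**The case against.** **The harm is conditional.** Section 14.2 neither names a denominator nor refers to 5.5.4, and the Section 2.2 wording fits an all-treated set at least as well. This stands. A reader might infer that the plan's ORR will be inflated; the documents support only that it would be raised or unchanged if the 5.5.4 set were used.

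**The rule is narrow and prespecified, and the effect is slight.** Most unscanned exits stay in the denominator. The number excluded may be reduced further, because Section 11.0 lists the Tumor Measurement Form at "Baseline, end of every even numbered cycles, and end of treatment" and Section 12.4.3 asks that progression be documented after treatment stops. Against that, the Section 10.0 calendar shows CT only at screening and after even-numbered cycles. So *k* cannot be read from the documents. That the shift is small also stands.

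**The phrase about disease assessment is undefined.** If the baseline scan counted, nobody would be excluded and ORR would not change. That reading would leave the clause almost empty, so it is read here as no on-study assessment, but the text does not say so.

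**Two further inferences go too far.** One is that the primary endpoint is compromised: 5.5.4 speaks of disease response and does not restrict PFS, which Section 12.4.5 defines from start of treatment. The other is that the continuation decision is biased across a boundary: 14.3 sets no response threshold, and it does not say that evaluable there means response-evaluable.

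**Conclusion.** The point holds as a conditional one. The direction is certain if the 5.5.4 set is the ORR denominator and if disease assessment means an on-study assessment. The size is not known, because the documents give neither the number excluded nor the number of responders. In the cases shown for 36 treated, the shift runs from zero to 2.1 points with up to 4 excluded, and reaches 3.3 points with 6 excluded and 6 responders. All of this is well inside the sampling uncertainty of an ORR in 36 patients.

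It is worth correcting because the shift runs one way, is tied to toxicity, and can be removed by wording before data are seen. It does not threaten the trial's primary conclusion.

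Section 5.4 asks for "additional patients will be enrolled for a total of 36 evaluable patients", while 14.1 writes "With a sample size of 36 patients including 3-6 patients from the phase I portion". That difference, and the unnamed analysis set for PFS, are separate clarifications and add no weight to this point.

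**What to change.** **Final analysis (Sections 5.5.4 and 14.2).** State that the primary ORR denominator is all patients at the RP2D who received any study treatment. Count patients with no post-baseline disease assessment as non-responders, and say that this is a convention. Report ORR in the 5.5.4 evaluable set as a sensitivity analysis, with the number excluded. State whether a baseline scan counts as a disease assessment under 5.5.4.

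**Interim look (Section 14.3).** Keep the phase II population, so that phase I patients treated at the RP2D are not added. Include treated patients who have reached their first scheduled scan or who came off study before it. Count the latter as non-responders if unscanned. Do not score patients whose first scan is not yet due.

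**Cost.** Wording in three sections, with no extra patients or procedures. The reported ORR may be slightly less favourable.

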## 5.6 General Concomitant Medication and Supportive Care Guidelines

Currently available *in vitro* data suggest that tosedostat may be a moderate inhibitor of selected catalytic activities of CYP3A4. Therefore, it may participate in or contribute to inhibitory drug-drug interactions *in vivo*, which are mediated by CYP3A4. Drugs that are known to be substrates for CYP3A4 include acetaminophen, carbamazepine, cyclosporin, digitoxin, diazepam, erythromycin, felodipine, fluoxetine, nifedipine, quinidine, saquinavir, triazolam, verapamil and warfarin. It is not expected, however, that tosedostat will reach sufficiently high, prolonged concentrations to significantly impact the metabolism of such drugs. Concomitant use of these drugs should be done with caution.

Due to the potential risk of cardiotoxicity, concomitant use of drugs that prolong the QT/QTc interval are prohibited (see Appendix C).

Due to the thrombocytopenic effects of capecitabine, an additive risk of bleeding may be seen in patients receiving concomitant anticoagulants and should be avoided. The manufacturer labeling for capecitabine includes a black box warning regarding concomitant use with warfarin. Administration of capecitabine concomitantly with Coumadin-derivative anticoagulants has resulted in prolonged coagulation parameters and/or bleeding; deaths have been reported. The interaction with warfarin is probably due to an inhibition of cytochrome P450 2C9 by capecitabine and/or its metabolites. If capecitabine is used with warfarin, close monitoring of the INR is necessary as dose adjustments may be necessary. If a patient is on enoxaparin or other anticoagulants, NSAIDs, or aspirin, use cautiously and discontinue with any bleeding episodes or if patient becomes thrombocytopenic.

Caution is advised when capecitabine is combined with phenytoin or fosphenytoin. Increased phenytoin plasma concentrations have been reported during concomitant use of phenytoin and capecitabine. Increased phenytoin plasma concentrations may be due to inhibition of cytochrome P450 2C9 by capecitabine and/or its metabolites. Patients taking phenytoin or fosphenytoin concurrently with capecitabine should be monitored for increased phenytoin plasma concentrations and associated clinical symptoms of phenytoin toxicity such as nystagmus, diplopia, ataxia, and confusion. A reduction in the phenytoin dosage may be required in some patients receiving concomitant capecitabine.

Patients should receive full supportive care during the study, including transfusion of blood and blood products, treatment with antibiotics, analgesics, erythropoietin, or bisphosphonates as appropriate. Anti-emetics (such as prochlorperazine, lorazepam, or other 5-HT3 antagonists) may be administered prophylactically in the event of nausea. Anti-diarrheals, such as loperamide, may be administered as needed in the event of diarrhea.

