### 3.2 Exclusion Criteria

1. Chemotherapy < 2 weeks prior to the first planned dose of study treatment.
2. Radiotherapy < 3 weeks prior to the first planned dose of study treatment.
3. A history of other malignancy  $\leq$  2 years previous with the exception of basal cell or squamous cell carcinoma of the skin which were treated with local resection only or carcinoma *in situ* of the cervix.
4. Currently receiving any other investigational agents.
5. Known brain metastases. Patients with known brain metastases must be excluded from this clinical trial because of their poor prognosis and because they often develop progressive neurologic dysfunction that would confound the evaluation of neurologic and other adverse events.
6. A history of allergic reactions attributed to compounds of similar chemical or biologic composition to tosedostat or capecitabine or other agents used in the study.
7. Previous treatment with any aminopeptidase inhibitor.
8. Previous exposure to either 5-FU or capecitabine at a systemic dose except for use in concurrent chemoradiation.
9. Known dihydropyrimidine dehydrogenase (DPD) deficiency or severe renal impairment (creatinine clearance < 30 mL/min by Cockcroft-Gault formula), as this would preclude use of capecitabine.
10. Significant cardiovascular disease defined as:
  - a. Myocardial infarction within 6 months of screening.
  - b. Unstable angina pectoris
  - c. Uncontrolled or clinically significant arrhythmia Grade  $\geq$  2
  - d. LVEF below institutional limits at screening
  - e. Congestive heart failure NYHA class III or IV
  - f. Presence of clinically significant valvular heart disease
11. Baseline troponin I or T > IULN and b-type natriuretic peptide > IULN.
12. Prior exposure to cardiotoxic agent, such as anthracyclines, within 3 months of enrollment.
13. Patient must have a QTc interval on ECG  $\leq$  0.48 seconds by Bazett's calculation at screening.

14. Patient may not be taking any drugs that prolong the QT/QTc interval (see Appendix C). If patient is on any of these drugs, patient may enroll in the study if the drugs can be discontinued for at least 5 half-lives prior to the first dose of tosedostat and capecitabine.
15. Uncontrolled intercurrent illness including, but not limited to, ongoing or active infection or psychiatric illness/social situations that would limit compliance with study requirements.

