### **5.1 Premedication Administration**

No premedications are required for either capecitabine or tosedostat. Anti-nausea medications can be used as per the treating physician's discretion.

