| Tosedostat                            |           |          | X G   |                |                                 |                |
| Capecitabine                          |           |          | X H   |                |                                 |                |
| Research blood for proteomics         |           | X        | X E   |                |                                 |                |
| Research blood for PKs (phase 1 only) |           |          | X F   |                |                                 |                |
| Archival tissue L          |           | X        |                  |                |                                 |                |
| Fresh biopsy                          |           |          |                  | X M |                                 |                |
| AE assessment N            |           | X        | X                |                |                                 | X              |

A: Every 3 months for 1 year

B: 1 month after end of study treatment, then every 6 months until the study closes

C: Women of childbearing potential only

D: ECG will be done weekly during Cycle 1. If ECGs are normal (or abnormal, but not related to study drug and/or clinically significant), ECGs will only be required on Day 1 of each cycle starting Cycle 2. However, if cycle 1 ECGs are abnormal and related to study drug, continue weekly ECGs.

E: Not drawn on C1D1

F: C2 only

G: Daily on Days 1-21 of each cycle

H: Daily on Days 1-14 of each cycle

I: Weekly during Cycle 1 of Phase I

J: The screening assessment will count as the C1D1 assessment

K: Echocardiogram preferred; prior approval from PI or designee required for MUGA

L: If available, archival tissue to be provided

M: Patients who have a PR will be required to undergo biopsy if deemed safe for the patient and tissue is feasible to obtain.

N: From baseline through 30 days after treatment ends.

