## APPENDIX C: List of QT Prolonging Medications

The following table presents a list of drugs that prolong, may prolong or are unlikely to prolong the QTc. Please note that this list is frequently updated. For the most current list of medications, users should be directed to the following website: <http://www.azcert.org/medical-pros/drug-lists/drug-lists.cfm>.

| Generic Name            | Brand Names                                                                                          | Risk Category               |
|-------------------------|------------------------------------------------------------------------------------------------------|-----------------------------|
| Albuterol (salbutamol)  | Proventil®, Ventolin®, Ventolin-HFA®, Accuneb®, Combivent®, Vospire-ER®, ProAir HFA®, Duoneb®        | Avoid in congenital long QT |
| Alfuzosin               | Uroxatral®                                                                                           | Possible Risk of TdP        |
| Amantadine              | Symmetrel®, Symadine®                                                                                | Conditional Risk of TdP     |
| Amiodarone              | Cordarone®, Pacerone®, Nexterone®                                                                    | Risk of TdP                 |
| Amisulpride             | Solian®, Supitac®, Soltus®, Amitrex®, Amazeo®                                                        | Conditional Risk of TdP     |
| Amitriptyline           | Elavil® (Discontinued 6/13), Tryptomer®, Tryptizol®, Laroxyl®, Saroten®, Sarotex®, Lentizol®, Endep® | Conditional Risk of TdP     |
| Amoxapine               | Asendin®, Amokisan®, Asendis®, Defanyl®, Demolox®, Moxadil®                                          | Conditional Risk of TdP     |
| Amphetamine             | Adderal-XR®, Dexedrine®, Dextroamp®                                                                  | Avoid in congenital long QT |
| Anagrelide              | Agrylin®, Xagrid®                                                                                    | Risk of TdP                 |
| Apomorphine             | Apokyn®, Ixense®, Spontane®, Uprima®                                                                 | Possible Risk of TdP        |
| Arformoterol            | Brovana®                                                                                             | Avoid in congenital long QT |

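### Section 5.6 bans QT-prolonging drugs, but its anti-emetic sentence taken on its face allows ondansetron, and the protocol does not say which rule governs

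*Combined protocol and SAP*

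**What the plan says.** Section 5.6 gives the risk of cardiotoxicity as its reason for the rule that "concomitant use of drugs that prolong the QT/QTc interval are prohibited (see Appendix C". Further on, its supportive-care paragraph names prochlorperazine, lorazepam and 5-HT3 antagonists as examples of anti-emetics and says that they "may be administered prophylactically in the event of nausea". Section 5.1 adds a general permission: "Anti-nausea medications can be used as per the treating" physician's judgment. Neither permission refers to Appendix C.

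Appendix C opens by describing its own scope: "The following table presents a list of drugs that prolong, may prolong or are unlikely to prolong the QTc". Each row then carries one of four risk labels. Ondansetron is labelled 'Risk of TdP'; granisetron and dolasetron are labelled 'Possible Risk of TdP'.

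At entry, exclusion 13 in Section 3.2 caps the screening QTc at 0.48 seconds ("Patient must have a QTc interval on ECG"). Exclusion 14 says "Patient may not be taking any drugs that prolong the QT/QTc interval (see Appendix C", with relief only through a washout of five half-lives before the first dose. During treatment, note D of the study calendar in Section 10.0 says "ECG will be done weekly during Cycle 1". If those tracings raise no drug-related concern, "ECGs will only be required on Day 1 of each cycle starting Cycle 2".

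**The concern.** The ban and the permission stand in one section, and at least one drug falls under both. A clinician who consults the supportive-care paragraph about a nauseated patient finds 5-HT3 antagonists allowed and could prescribe ondansetron, which the earlier paragraph of 5.6 prohibits on safety grounds.

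The situation is foreseeable. The DLT definition in Section 5.5.2 makes specific allowance for Grade 3 nausea and vomiting, so the protocol expects some patients to need treatment for them. It also takes cardiac risk seriously: the study rationale in Section 1.4 caps tosedostat at 120 mg daily because of cardiac events in other trials of the drug. What is at stake is the safety of individual patients and consistent conduct, not an error rate or an estimate.

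**Working it through.** The plan states no figure on this point, so there is none to reproduce. The check sets the texts side by side and counts rows in Appendix C. One fact comes from general pharmacology, because the documents do not classify the agents: ondansetron, granisetron and dolasetron are 5-HT3 antagonists.

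**1. The rules as they apply to an anti-emetic started during treatment**

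| Place | Rule | Excepts Appendix C agents? |
|---|---|---|
| 5.6, QT paragraph | QT-prolonging drugs banned, by reference to Appendix C | It is the ban |
| 5.6, supportive care | 5-HT3 antagonists allowed as a class | No |
| 5.1 | Anti-nausea drugs at the physician's discretion | No |
| 3.2, exclusion 14 | QT-prolonging drugs barred at entry | Concerns drugs in use at entry, so it does not settle a later start |

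Sections 3.2, 5.1 and 5.6, the study calendar and Appendix C contain no precedence rule, no exception and no ECG condition tied to an anti-emetic.

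**2. How far the overlap goes**

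The ban does not say which Appendix C categories it covers, and the appendix states that its list extends to drugs unlikely to prolong the QTc. Two scopes are therefore worth counting.

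- Ban limited to 'Risk of TdP': 42 rows. Ondansetron is among them, so 1 of the 3 listed 5-HT3 antagonists conflicts.
- Ban extended to 'Possible Risk of TdP': 42 + 65 = 107 rows. Granisetron and dolasetron are added, so 3 of 3 conflict.
- Prochlorperazine and lorazepam: 0 rows in the printed list.

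Ondansetron is caught under either scope. The other two depend on a scope that the protocol leaves open.

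**3. What the ECG schedule can catch**

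Cycles last 21 days. Weekly tracings give 21 / 7 = 3 ECGs in Cycle 1, 7 days apart. From Cycle 2, if Cycle 1 raised no drug-related concern, there is 1 per cycle, nominally 21 days apart. No ECG is triggered by starting an anti-emetic. The schedule is a partial backstop: it can show prolongation after exposure but does not prevent the exposure.

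**The case against.** The strongest reply is that there is no true contradiction. The ban is specific, gives a safety reason and points to a named list. The permission is a general supportive-care clause with illustrative examples, and permission to use a class need not license a member that the same section bans. The paragraph itself supports this reading: it also allows antibiotics without exception, although Appendix C labels azithromycin, clarithromycin, levofloxacin and moxifloxacin 'Risk of TdP'. Presumably those were not meant to be licensed either. The anti-emetic sentence is also loosely drafted, since its wording treats prochlorperazine and lorazepam as if they were 5-HT3 antagonists, and it never names ondansetron.

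Much of this stands. A reader might infer that ondansetron is both allowed and forbidden however the text is read. The documents do not support that, because letting the ban govern is an ordinary and safer reading. What the reply cannot supply is a sentence in the protocol that says so. The antibiotic example shows that the gap is wider than anti-emetics. So does the paragraph of 5.6 on CYP3A4, which asks only for caution with a list that includes erythromycin and quinidine, both 'Risk of TdP'.

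It is also fair to say that the harm cannot be sized. The cardiac events listed in Section 1.4 do not include QT prolongation, and the pharmaceutical information on tosedostat is blacked out. Row counts and ECG intervals describe the wording and the monitoring, not patient risk.

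**Conclusion.** The concern holds as a conflict of wording that bears on patient safety. On its face the anti-emetic sentence of 5.6 permits ondansetron, the QT paragraph of 5.6 prohibits it, and nothing states which governs. A correction should be made, because a clinician following the stated permission could give a drug banned for safety reasons and the remedy is cheap.

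Three stronger inferences are not supported:

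- That the protocol forces a breach. Both rules can be followed together with prochlorperazine, lorazepam or any unlisted agent.
- That all three listed 5-HT3 antagonists are certainly in conflict. For granisetron and dolasetron this needs a ban that reaches 'Possible Risk of TdP'.
- That the trial's statistics are affected. The sample size and the PFS analysis do not depend on this point.

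The conclusion assumes the printed Appendix C. The appendix says that its list is often updated and refers to a website for the current one, so the status of a single agent could change.

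**What to change.** In the anti-emetic sentence of 5.6 and in 5.1, add: *except agents prohibited under Appendix C (at minimum those labelled Risk of TdP, e.g. ondansetron)*.

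In 5.6, also state that the QT ban takes precedence over the other permissions in that section, and name the Appendix C risk categories that it covers. The precedence statement deals with the antibiotics and with the drugs now allowed with caution. The scope statement settles granisetron and dolasetron.

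If the sponsor in fact wanted a supportive-care exception, the text should say so, name the permitted agent and require an ECG after it is started.

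The main fix changes wording only and adds no procedure. Its small downside is a narrower choice of anti-emetics, which the existing ban already implies. The alternative would add an ECG for each patient who starts the excepted drug.
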